10.4 Statistical/Analytical Methods

Statistical analyses will be performed by an external CRO, managed by the sponsor's Biometry Department.

A SAP describing the planned statistical analysis in detail with tables, figures and listings (TFLs) templates will be developed as a separate document.

The SAP will detail the rules and conventions used to compute the derived analysis variables and to handle missing data

Statistical evaluation will be performed using Statistical Analysis System (SAS)[®] (version 9.2 or higher).

Descriptive statistics will be presented as follows:

- continuous variables: number of observations, number of missing values mean, standard deviation (SD), median, percentiles, minimum and maximum,
- dichotomous or categorical variables: frequency and percentage of each of the categories.

No adjustments for multiple testing are planned.

All study data will be at least presented in listings.

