10.4.5 Efficacy Evaluation

The primary analysis of efficacy data will be performed on the ITT population. Additionally, for the main efficacy variable, a supportive analysis using mITT and PP populations will be carried out.

The primary endpoint (time from the first study treatment intake (T_0)) to recovery defined as 1st formed stool followed by a nonwatery stool (in hours), will be analysed using a time to event methodology.

Time to event data will be analysed by using survival methods. The results will be presented both in summary tables and graphically in Kaplan-Meier plots and the estimated medians and quartiles will be provided.

The comparison between the 2 groups of treatment will be performed using Gehan-Wilcoxon test. Subject prematurely withdrawn or ending the study without recovery will be censored (not responder).

Sensitivity analyses will be conducted to further explore the primary efficacy endpoint adjusting by country.

A cox model [14] will be used to assess the impact of other factors like season of randomisation, absence/presence of faecal pathogens on the treatment effect.

The analysis regarding secondary efficacy endpoints will be performed on the ITT population; supportive analysis using PP population will be carried out.

The secondary efficacy variables are:

- a) Abdominal pain intensity per 12-hour period.
- b) Time (hours, minutes) from diarrhoea onset to recovery defined as 1st formed stool followed by a nonwatery stool.
- c) Time (hours) from first watery stool to the first formed stool.
- d) Time (hours) from the 1st study treatment intake to the last watery stool.
- e) Number of stools, per 12-hour period.
- f) Number of watery stools, per 12-hour period.
- g) Percentage of subjects with associated symptoms such as nausea, vomiting, abdominal pain and anal irritation, per 12-hour period.

Missing data of secondary efficacy variables will not be replaced.

The secondary endpoints related to time to event (efficacy variables b, c and d) will be analysed using the same methodology as for the primary efficacy endpoint.

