- and/or pus or blood in the stool
- and /or positive microbiological finding for Entamoeba histolytica or Giardia/Lambliia or Shigella in stool,

the subject will be withdrawn from the study and an effective rehydration therapy and/or an anti-parasitic or antibiotic treatment will be immediately given accordingly.

If the subject is discontinued from the study (i.e. ceases participation in the study prior to completion of the protocol), the reason will be recorded in the eCRF.

Withdrawal due to AEs should be distinguished from other conditions for withdrawal. The investigator will record the reason for study discontinuation, provide or arrange for appropriate follow up (if required) for such subjects, and document the course of the subject's condition. In all cases, the investigator must ensure the subject receives appropriate medical treatment (i.e. need for IV rehydration, and/or antiparasitic, and/or antibiotic therapy) and follow up to determine the final outcome if the period of the trial is over.

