1.3.4 Planned sample size

Assuming a median time to recovery of 55 hours in the active group and 70 hours in the placebo group (corresponding to a difference of 15 hours as evidenced in the Khediri et al study [1]), 363 evaluable subjects per treatment group (726 in total) will be required in order to detect such a difference using a two-sided Gehan-Wilcoxon test at a significance level of 5% and a power of 80%.

It is assumed a maximum of 5% of subjects prematurely withdrawn without recovery and a maximum of 10% of non-evaluable subjects (because of poor/incomplete diary completion). Accordingly, 854 subjects (427 per treatment group) will be required in order to achieve an 80% power.

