3.1.4 Multiplicity

No adjustments for multiple testing are planned. Only primary analysis of the primary endpoint (ITT population) will be considered confirmatory.

3.1.5 *Significance testing and estimation*

All statistical tests will be performed two-sided with a type I error rate set at (5%). For any efficacy endpoints, the 95% confidence interval (CI) of the difference between treatment groups will be calculated when appropriate.

3.2 **Analysis methods**

3.2.1 *Efficacy*

3.2.1.1 *Primary efficacy analysis*

(a) Main analysis

The primary analysis of efficacy data will be performed on the ITT population.

The primary endpoint (time from the first study treatment intake (T0)) to recovery defined as 1st formed stool followed by a nonwatery stool (in hours), will be analysed using a time to event methodology.

Any stool recorded before dosing should not be taken into account in the analysis.

The time to recovery will be given in hours and will be analyzed using the Kaplan Meier (KM) survival analysis method (see SAS syntax hereafter). The median recovery time, first and third quartiles with their 95% CIs will be estimated for each treatment group using KM product-limit estimation. In addition, KM cumulative estimators will be computed for recovery rates at 12, 24, 36, 48, 60, 72, 84, 96 hours and estimates for every 12 hours thereafter as applicable.

Results will be also presented graphically in Kaplan-Meier plots.

The primary analysis will test the equality of time to recovery between the two treatment groups, applying the two-sided Gehan-Wilcoxon test ($\alpha = 5\%$) based on the ITT set.

The following Null-hypothesis is tested:

$$H_0: \lambda_A(t) = \lambda_B(t) \text{ versus } H_1: \lambda_A(t) \neq \lambda_B(t),$$

where $\lambda(t)$ represents the hazard at time t, A=diosmectite and B=placebo.

CCI

Subjects prematurely withdrawn without recovery or ending the study without recovery will be censored (not responder) at their last date/time of stools as recorded in the DEB.

Special cases of censoring: subjects who have not filled in the DEB (i.e. no post baseline evaluation regarding "stool number" and "consistency" according to Bristol scale) will be censored at the date and time of their first study drug intake (or the randomisation date time if not administered).

A frequency table of reasons of censoring will be displayed by treatment group.

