3.2.1.2 Secondary efficacy analysis

The analysis regarding secondary efficacy endpoints will be performed on the ITT population. Supportive analysis using PP population will be carried out if more than 10% of subjects are excluded from ITT set.

Rules for handling incomplete dates and times recorded on the DEB are described in section 3.2.3.2.

(a) Abdominal pain intensity per 12-hour period

Intensity of abdominal pain per 12-hour period will be summarized by treatment group (an absence of pain will be considered as value zero).

Considering the ordinal nature of the outcome, difference between diosmectite and placebo will be studied by fitting a cumulative logit model assuming an ordered multinomial response distribution. The model will include treatment group as fixed effects and a random intercept effect. Contrasts between diosmectite and placebo will be given in term of odds ratios (modelling the probabilities to obtain higher scores of pain intensity). The model will be performed for each time point (12-hour period) separately (see SAS Syntax below).

CCI
[Redacted]

(b) Time from diarrhoea onset to recovery

This endpoint is a time to event endpoint which will be analysed using the same methodology as for the primary efficacy endpoint. The date and time of diarrhoea onset will be the start date and time of diarrhoea onset as recorded from the "History

of current acute diarrhoea episode” eCRF section. Subjects will be censored using the same rules as defined for the primary endpoint.

(c) Time from diarrhoea onset to the first formed stool.

This endpoint is a time to event endpoint which will be analysed using the same methodology as for the primary efficacy endpoint.

(d) Time from the 1st study treatment intake to the last watery stool.

This endpoint is a time to event endpoint which will be analysed using the same methodology as for the primary efficacy endpoint.

(e) Number of stools, per 12-hour period.

Number of stools per 12-hour period (0-12h, 12-24h, 24-36h...) will be computed by summing the number of stools as recorded in the DEB by the subject using the time (24-hour clock) of visit to restrooms. The number of stools per 12-hour period will then summarized by treatment group. From first to last intake, if no stool is reported in the diary at a specific time interval, the number of stools at the considered 12-hour period will be considered as zero.

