- Time from diarrhoea onset to recovery (hours) will be calculated as follows:

(Date/time of Recovery or last date/time of stool (if censored) – date/time of diarrhoea onset).

The date and time of diarrhoea onset will be the start date/time of first unformed loose or watery stool as recorded in the “History of current acute diarrhoea episode” eCRF page.

Rules of censoring are the same as described for primary endpoint.

- Time from diarrhoea onset to the first formed stool (hours) will be calculated as follows:

(Date/time of 1st formed stool or last date/time of stool (if no formed stool) – date/time of diarrhoea onset).

The date of 1st formed stool will be the earliest date of stools with a formed consistency corresponding to type 1 to 4, whatever the consistencies of the next stools.

Rules of censoring are described in the table below:

Event	Decision	Date of event or censoring to consider for the analysis
Formed stool	Not censored	Earliest Date/time of formed stool
No formed stool and subject completed the study	Censored	Date/time of last stool
No formed stool and subject prematurely withdrawn the study	Censored	Date/time of last stool
No formed stool and no post-baseline evaluation of stools	Censored	Date/time of first IMP intake (if administered)
		Date/time of randomisation (if not administered)

- Time from the first study treatment intake to the last watery stool (hours) will be calculated as follows:

(Date/time of last watery stool or last date/time of stool (if censored) – date/time of 1st treatment intake).

The date of last watery stool will be the latest date of stools recorded by the subject, with a consistency corresponding to type 6 or 7.

Rules of censoring are described in the table below:

Event	Decision	Date of event or censoring to consider for the analysis
Watery stool	Not censored	Date/time of last watery stool

SAP Final Version: 15 July 2019

34/50

Event	Decision	Date of event or censoring to consider for the analysis
No watery stool and subject completed the study	Censored	Date/time of last stool
No watery stool and subject prematurely withdrawn the study	Censored	Date/time of last stool
No watery stool and no post-baseline evaluation of stools	Censored	Date/time of first IMP intake (if administered)
		Date/time of randomisation (if not administered)

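### Time to last watery stool (secondary, non-confirmatory): the SAP table scores continuing watery stools as events and censors subjects who had none after dosing

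*SAP*

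**What the plan says.** The decisive text is the censoring table for this endpoint in SAP 3.2.12 (Derived data). Its first row takes any subject with a watery stool and codes the observation as not censored, at the date and time of the last one. The rule above the table reads "The date of last watery stool will be the latest date of stools recorded by the subject", limited to Types 6 and 7. Neither the rule nor the row asks whether watery stools had stopped, or whether the subject recovered, completed or withdrew.

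The next rows cover subjects without a watery stool. "No watery stool and subject completed the study" is censored at the last stool, and so is the matching row for premature withdrawal. Subjects with no post-baseline stool evaluation are censored at first intake, or at randomisation if not dosed. SAP 3.2.1.1 excludes stools recorded before dosing, so only post-dose stools count.

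SAP 3.2.1.2 lists the endpoint as "d) Time from the 1st study treatment intake to the last watery stool" and gives it the primary endpoint's methodology. Protocol 10.4.5 says the same: "efficacy variables b, c and d) will be analysed using the same methodology as for the primary efficacy endpoint". In the primary analysis, a subject who withdraws or finishes without recovery is censored. Protocol 10.4 also states: "The SAP will detail the rules and conventions used to compute the derived analysis variables and to handle missing data". SAP section 5 lists no changes from the protocol.

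On status, SAP 3.1.4 says: "Only primary analysis of the primary endpoint (ITT population) will be considered confirmatory".

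**The concern.** Coding an observed occurrence as an event and its absence as censored is right for a first occurrence, such as the first formed stool in the same SAP section. For a last occurrence it reverses the meaning. A recorded watery stool shows only that the last one is no earlier than that. It becomes the last one once later follow-up shows that watery stools ceased.

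The affected cases are foreseeable. SAP 1.3.2.4 lists dehydration, impaired general condition, fever, and blood or pus in the stool as grounds on which "the subject will be withdrawn from the study and an effective rehydration therapy" follows. SAP 1.3.4 plans for such losses: "It is assumed a maximum of 5% of subjects prematurely withdrawn without recovery". Subjects not recovered at Visit 2 go on to Visit 3, and some may still have watery stools then. The table's own rows foresee completers with no watery stool.

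At stake is what the Kaplan-Meier curve for this endpoint means and, if the arms differ in these cases, the direction of its test.

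**Working it through.** **1. The table applied to each kind of subject**

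| Subject | What is known | SAP table |
|---|---|---|
| Watery stools stopped, then recovery | Last watery stool observed | Event at that stool (correct) |
| Withdrawn with watery stools continuing | Last watery stool not yet seen | Event, often early |
| Watery stools continuing at Visit 3 | Last watery stool not yet seen | Event |
| No watery stool after dosing, recovered or completed | Already past the last watery stool at first intake | Censored at last stool, as if the event were still to come |

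The fault follows from this reading alone. The rest concerns size.

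**2. The plan's own figure.** The plan states no power or event count for this endpoint. For the primary endpoint, HR = 55/70 = 0.786, and log-rank events = 4(1.960 + 0.842)²/(ln 0.786)² ≈ 540 (546 by Freedman's formula). Dividing by 0.75, the efficiency of Gehan-Wilcoxon relative to log-rank under proportional hazards without censoring, gives 720 to 728, against the stated 726. Then 726/0.85 = 854.1, against the stated 854. Both reproduce, and neither depends on the table at issue.

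**3. Simulation model.**
- From the plan: 427 per arm, two-sided Gehan-Wilcoxon test at 5%, 5% withdrawn before recovery, and 55/70 h as a scale.
- Assumed: exponential time to last watery stool (55/70 h, or 62/62 h for no difference); watery-stool gap mean 4 h; first formed stool mean 10 h after the last watery one; confirming stool mean 12 h later; Visit 2 at 96–144 h; Visit 3 at 192–216 h; withdrawal uniform over 6–96 h or at constant hazard.
- Test: U = Σ nⱼ(d₁ⱼ − dⱼn₁ⱼ/nⱼ), rejecting if |U/√V| > 1.96.
- Runs used 1,500 to 3,000 replicates. Ranges cover separate runs and both withdrawal patterns.

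**4. Share still having watery stools when observation ends.** Using 55/70 h for the last watery stool makes recovery later than planned. With μ = median/ln 2, P(recovery > t) = (μe^(−t/μ) − 10e^(−t/10))/(μ − 10). For diosmectite μ = 79.35 and this equals 0.50 at t = 65.7 h. The simulated recovery medians were 65.7/80.7 h, not 55/70 h. Restoring the plan's medians shortens the last-watery-stool medians by about 10.7 h, to 44.3/59.3 h. At the middle of the assumed Visit 3 window (204 h):
- unadjusted: 0.5^(204/55) = 7.6% and 0.5^(204/70) = 13.3%; simulated, after withdrawals, 7.1%/12.5%
- restored: 0.5^(204/44.3) = 4.1% and 0.5^(204/59.3) = 9.2%; simulated 4.2%/9.0%

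Adding those withdrawn with watery stools continuing (3.9%/4.1%, from the unadjusted runs) gives 4.2 + 3.9 = 8.1% and 9.0 + 4.1 = 13.1%. A steeper distribution (Weibull shape 1.5) with restored medians leaves only 0.1%/1.3% at Visit 3.

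**5. Effect on the test** (diosmectite/placebo; last-watery-stool medians 55/70 h unless stated; the corrected rule is the one under the fix)

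| Scenario | SAP table | Corrected rule |
|---|---|---|
| Withdrawal 5%/5%: power | 81–84% | 82–83% |
| Same, recovery medians restored: power | 92.5% | 92.7% |
| Withdrawal 5%/5%, 62/62 h: rejection | 4.3–4.4% | 4.2–4.7% |
| Withdrawal 3%/7%, 62/62 h: false wins for the 7% arm (nominal 2.5%) | 7–10% | about 2% |
| Same: false wins for the 3% arm | – | about 3.4% |
| No post-dose watery stool 4%/2%: power | about 70% | about 91% |
| No post-dose watery stool 5%/5%: power | 78–80% | 74–75% |

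The unequal withdrawal rates, and all shares with no post-dose watery stool, are assumptions. None comes from the documents.

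**The case against.** The strongest defence is literal. Protocol 3.2.2 and SAP 3.1.2 define the endpoint by the last watery stool recorded in the diary. On that wording every subject with a recorded watery stool has an observed value, and the first row implements it. This stands as a description: the result is then the time of the last recorded watery stool, not of cessation. It does not fit easily with the primary methodology named in SAP 3.2.1.2 and Protocol 10.4.5. Nor does it rescue the rows without a watery stool: on either reading, a completer with none is not still waiting for one.

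Second, the effect on the test is negligible unless the arms differ, and nothing in the documents predicts that they will. One withdrawal trigger, a positive finding for named pathogens, comes from a stool taken soon after inclusion and should be roughly balanced. SAP 3.2.5 tabulates withdrawals and their reasons by arm, so an imbalance would be visible. Protocol 1.4 expects most episodes to last under 8 days, with few late censored observations. All of this stands and keeps the severity low.

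Third, the corrected rule has costs of its own. This also stands; they are listed under the fix.

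A reader might infer that the SAP contradicts the protocol. The documents do not establish this, because Protocol 10.4 leaves derivation rules to the SAP. The statement about methodology and the table need to be reconciled.

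**Conclusion.** The point holds, at low severity. For a last-occurrence endpoint the table scores subjects with continuing watery stools as resolved, and the best outcomes as unresolved. If every subject has a watery stool after dosing, the curve must reach 100% in both arms, whatever the share still unwell.

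With exponential times and the plan's recovery medians, about 8%/13% of subjects would be scored as events with watery stools continuing. Steeper distributions give fewer. With balanced arms the test is almost unchanged. Bias needs an imbalance: extra withdrawals help an arm, and extra subjects with no post-dose watery stool hurt it.

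A reader might conclude that the table favours diosmectite. The documents give no arm-specific rates, so no direction can be claimed. Nor is the table always the less powerful rule, as the 5%/5% scenario shows. The primary analysis and the sample size are unaffected.

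**What to change.** Before unblinding, replace the SAP 3.2.12 table for this endpoint:

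- **(a) Event** at the last Type 6–7 stool if the subject later met the recovery definition with no further Type 6–7 stool, or completed the final visit with the diary kept and no Type 6–7 stool in a pre-specified period before it (for example 24 h). Do not require a later stool: Protocol 1.4 names constipation as the most frequently described side effect, and SAP 3.2.1.1(f) already foresees a formed last stool with none after it.
- **(b) Otherwise censor** at the last Type 6–7 stool.
- **(c) No post-dose Type 6–7 stool:** event at a minimal positive time (for example 1 minute) if the subject recovered, or completed the final visit with the diary kept. Otherwise censor at first intake, or at randomisation if not dosed.

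Keep the current table as a sensitivity analysis. If it is retained as the main rule on purpose, say so in SAP section 5 and label the result as time to last recorded watery stool.

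The change needs wording and some recoding, and no new data. Its downsides should be stated:
- Fewer events: about 83% of subjects instead of 100% with exponential times at 55/70 h, and 92% with Weibull shape 1.5.
- A modest tilt against the arm with more withdrawals, because (b) also censors subjects whose watery stools had stopped before they withdrew.
- Somewhat lower power if equal shares of both arms have no post-dose watery stool.
- A period in (a) that must be fixed in advance. Using 12 h or 48 h left simulated power at about 82%.

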3.2.15 Pooling of Centres

Regarding the primary endpoint, it is planned to assess and adjust the treatment comparison by computing the median of time to recovery for diosmectite and placebo for each country (subgroups analysis).

Subjects are planned to be recruited in seven countries: Algeria, Czech Republic, Egypt, Lebanon, Poland, Romania and Tunisia.

3.2.16 Interim analysis

No interim analysis will be performed.

3.2.17 Role of independent data monitoring committee (DMC)/interim data review committee [if applicable]

No independent data monitoring committee/interim data review committee will be used in this study.

3.2.18 Covariates and analysis of subgroups

Subgroups analyses on the primary endpoint are planned for the following group of variables:

Time since diarrhoea onset

- \leq median (reference)
- $>$ median

Country (largest country to be used as reference)

- Algeria
- Czech Republic,

SAP Final Version: 15 July 2019

39/50

- Poland,
- Tunisia
- Egypt
- Lebanon

Season of randomisation:

- Winter (reference)
- Summer

Virology subgroup:

- Positive (reference): at least Presence of one of the following:
 - (a) Adenovirus ,
 - (b) Rotavirus,
 - (c) Norovirus,
- Negative: no presence and at least one absence among all above tests
- Not done or missing result for all tests.

Bacteriology subgroup:

- Positive (reference): at least Presence of one of the following:
 - (a) Enteropathogenic or enterotoxigenic E. Coli
 - (b) Staphylococcus aureus,
 - (c) Shigella,
 - (d) Salmonella,
 - (e) Campylobacter,
 - (f) Yersinia enterocolitica,
- Negative: no presence and at least one absence among all above tests
- Not Done or missing result for all tests.

Parasitology subgroup:

- Positive (reference): at least Presence of one of the following:
 - (a) Aemibiasis (entamoeba histolytica)
 - (b) Giardia/lamblia
- Negative: no presence and at least one absence among all above tests
- Not done or missing result for all tests.

Covariables used in mixed models will be:

- Number of stools 24 hours before randomisation (baseline) as recorded in the “History of current acute diarrhoea episode” eCRF page and calculated as follows: Number of stools during the first 12-hour period + Number of stools during the second 12-hour period.
- Number of watery stools 24 hours before randomisation (baseline) calculated as follows: Number of watery stools during the first 12-hour period + Number of watery stools during the second 12-hour period.

Missing values will not be replaced.

4 COMPUTER SYSTEMS, SOFTWARE AND VALIDATION OF PROGRAMS**4.1 Hardware**

The statistical analysis will be performed using a computer on a Windows 7 operating system.

